#### **5.7. Administration and Accountability**

The investigational products will be checked on receipt as above ([Section 5.3](#)). Prior to administration, PMT-001 and PMT-002 will be allowed to thaw at room temperature ( $50^{\circ}\text{F}$  -  $75^{\circ}\text{F}$ ) for 30-60 minutes. The bag may be massaged during thawing. Administration of PMT-001 and PMT-002 will begin within 60 minutes of thawing. Prior to administration, PMT-003 will be kept on dry ice; PMT-003 will not be thawed before administration.

As stated in [Section 5.4](#), the total time from release from frozen storage at the manufacturing facility to initiation of administration will not exceed 180 minutes for PMT-001 and PMT-002; it will not exceed 120 minutes for PMT-003.

The duration of administration will take 10 - 90 (target 30) minutes for all products. Administration of all three PMT products will be performed by a licensed physician, advanced medical practitioner, or nurse.

PMT-001 will be administered by enema using an approved enema administration kit. PMT-002 will be administered via intragastric, intraduodenal, or intrajejunal route, contingent on the presence of a pre-existing approved intragastric, intraduodenal, or intrajejunal tube. PMT-003 will be administered orally. Post-procedure monitoring will be performed as described elsewhere. For each investigational product dose, the product identity, dose targeted for administration, the date and time administered, route of administration, subject identity, quantity of product actually administered, and quantity of product remaining will be recorded via a standard form.

### **5.8. Subject Compliance Monitoring**

Post-procedure monitoring will be performed as described elsewhere ([Sections 3.1.3 to Section 3.1.5](#)). For each investigational product dose, the product identity, dose targeted for administration, the date and time administered, route of administration, subject identity, quantity of product actually administered, and quantity of product remaining will be recorded via a standard form. The study team will record if the subject was not able to tolerate or receive the full dose due to adverse events or because the allowed duration of administration was exceeded.

### **5.9. Return or Destruction of Investigational Product**

For PMT-001 or PMT-002, the volume of investigational product will be recorded at the time of drug product manufacturing, and the volume of residual investigational product (if any) will be recorded by the licensed medical professional performing administration after administration is completed (or stopped). For PMT-003, the number of capsules in the dose will be recorded at the time of drug product manufacturing, and the number of remaining capsules (if any) will be recorded by the licensed medical professional performing administration after administration is completed (or stopped). Any remaining investigational product will be disposed of at the clinical site.

## **6. Study Procedures**

The study procedures are also outlined in detail below. The schedule of study procedures is presented in [Table 3](#).

### **6.1. Screening and Enrollment**

#### **6.1.1. Surveillance Test Review**

Potential subjects will be identified by active surveillance for inpatients at participating hospitals with positive *C. difficile* EIA stool testing.

#### **6.1.2. Medical Record Review for Inclusion/Exclusion Criteria**

A positive stool EIA test for *C. difficile* will prompt review of the electronic health record to determine whether a potential subject may meet inclusion/exclusion criteria ([Sections 4.1 and 4.2](#)).

#### **6.1.3. Informed Consent**

If a potential subject may meet inclusion/exclusion criteria, the study team will contact the subject's inpatient care team to ascertain whether the care team has any objection to the study team enrolling the potential subject. The potential subject (or their designated medical decision-maker) will be contacted to discuss participation. If the potential subject is eligible and wants to

participate, informed consent will be obtained. Subjects of childbearing potential will be tested using a urine pregnancy test if possible; if urine pregnancy test positive or not possible, potential subjects will be excluded. A record of all screened subjects will be maintained to evaluate the frequency of identified exclusions or care-team objections.

#### **6.1.4. Enteral Access Check**

The enrolled subject's enteral access will be reviewed to determine whether the subject qualifies for randomization between upper and lower gastrointestinal delivery of investigational product.

#### **6.1.5. Randomization**

Following enrollment, randomization will be performed as per [Section 3.1.6](#).

### **6.2. Study Intervention Phase**

#### **6.2.1. PMT Product Receipt**

After the treatment plan is determined by randomization, the PMT product to which the subject is assigned will be prepared and received as described above ([Section 5.3](#)).

#### **6.2.2. Administration**

During the intervention period, following informed consent and randomization, subjects in either intervention arm (not the standard of care control arm) will receive single-dose PMT administration, with the PMT formulation determined per randomization. Administration of the product (PMT-001, PMT-002, or PMT-003) will take place over 10 to 90 minutes (target 30 minutes). Subjects will be eligible to receive up to two additional administrations of PMT at 3-day intervals, if they fail to meet criteria for clinical improvement. Antibiotics prescribed as part of routine clinical care for CDI will not be altered by the intervention.

#### **6.2.3. Post-Intervention 60 minutes**

Subjects will be monitored for a period of 60 minutes following completion of PMT administration. Subjects will be visually observed for signs of aspiration or other respiratory distress, abdominal pain, vomiting, other signs of allergic reaction, and changes in vital signs. Vital signs (temperature, heart rate, respiratory rate, blood pressure, and oxygen saturation) will be checked immediately post-administration and at 30 and 60 minutes following completion of PMT administration. The following vital sign changes will be recorded if observed, and will prompt notification of the primary clinical care team: (1) increase or decrease by greater than or equal to 30 beats per minute; (2) respiratory rate increase or decrease by greater than or equal to 10 breaths per minute or if respiratory rate drops below 10 or increases above 25 (if respiratory rate not already outside these ranges); (3) temperature: increase or decrease by greater than or equal to 2 degrees Fahrenheit, or if temperature drops below 96°F or increases above 100.4°F (if temperature not already outside these ranges); (4) oxygen saturation decrease by greater than or equal to 5% (sustained for more than 20 seconds) or if oxygen saturation drops below 90% (on current amount of oxygen delivered, sustained for more than 20 seconds); (5) blood pressure decrease by more than 30 mmHg systolic or 15 mmHg diastolic, or if blood pressure drops below 90/60 (if blood pressure not already outside these ranges).

#### **6.2.4. Post-Intervention 3 Days**

The subject will be monitored every calendar day for three days after each PMT administration in order to assess their eligibility for repeat up to 2 additional doses of PMT at 3 days after the first administration and 3 days after a second administration (if given) as well as to assess for adverse events. If the subject continues to meet criteria for severe or severe-complicated disease within the prior 24 hours at 3 after the initial administration and 3 days after a second administration (if given) (see [Section 3.2.1](#)) and if the subject has not undergone bowel surgery, the subject will be eligible for an additional dose of PMT (formulation per repeat assessment of subject's mode of nutrition and medication – i.e., change in formulation is allowed). If PMT administration is unable to be performed on the scheduled days, administration within 1 calendar day before or after those days will be permitted. Subjects will be assessed for eligibility for an additional dose on the day of repeat administration. Subjects in the non-PMT arm will be monitored every calendar day for three days after enrollment to assess for adverse events.

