### **1.3. Dose Rationale**

There are no pre-clinical or clinical data for the PMT suite of FMT products to inform optimal dose. However, there are extensive observational studies and several randomized trials that suggest an FMT dose derived from 30-100g of human stool is effective to treat R-CDI (Cammarota 2014; van Nood 2013; Youngster JAMA 2014; Kelly CR 2016). Protocols for the treatment of S/SC/F-CDI have typically used similar FMT doses as protocols for the treatment of R-CDI, but have allowed for repeat FMT administration at short intervals if clinically indicated (Weingarden 2013; Agarwal 2015; Aroniadis 2015; Fischer 2015; Fischer 2017). See [Table 1](#) for a summary of doses described in the literature.

The S/SC/F-CDI trial protocol allows for repeat PMT dosing at 3-day intervals, up to a maximum of three doses, if subjects fail to meet pre-established criteria for clinical improvement. The repeat administration strategy is based on the observation that some patients with S/SC/F-CDI fail to improve with initial FMT administration but do improve after repeat administration (Weingarden 2013; Agarwal 2015; Aroniadis 2015; Fischer 2015; Fischer 2017).

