## **3. Investigational Plan**

### **3.1. General Design**

We will perform a randomized, controlled, open label trial. Subjects will be screened to evaluate if they meet inclusion criteria for severe or severe complicated/fulminant CDI. If eligible, subjects will participate in the informed consent process. Following informed consent, subjects

will be randomized to one of three arms: (1) standard of care antibiotics (no intervention), (2) PMT-upper GI administration plus standard of care antibiotics, or (3) PMT-lower GI administration plus standard of care antibiotics. Subjects will then be eligible to receive up to two additional administrations of PMT (upper or lower GI) at 3-day (+/- 1 day) intervals if they do not meet pre-defined criteria for clinical improvement (see [Section 3.2.1](#) below). Subjects will be followed until 180 days after their last PMT dose.

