### **3.1.2. Study Intervention Phase**

All S/SC/F-CDI trial interventions will be performed inpatient at the listed study site hospitals. During the intervention period, following informed consent and randomization, subjects in either the upper GI (PMT-002 or PMT-003) or lower GI (PMT-001) intervention arm will receive single-dose PMT administration, with PMT formulation and route of administration (suspension for enema, suspension for enteric delivery, or oral capsules) determined per randomization and stratification scheme ([Section 3.1.6](#)). Administration of the product will take place over 10 to 90 minutes (target 30 minutes). Subjects randomized to PMT will be eligible to receive up to two additional administrations of PMT (by clinically appropriate route of administration) at 3-day (+/- 1 day) intervals, if they fail to meet criteria for clinical improvement ([Section 3.2.1](#)). Antibiotics prescribed as part of routine clinical care for CDI will not be altered by the intervention.

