#### **3.1.4. Post-PMT Administration monitoring: Daily for 3 Days after Administration/Enrollment**

The subject will be monitored every calendar day for three days after each PMT administration in order to assess their eligibility for repeat up to 2 additional doses of PMT at 3 days after the first administration and 3 days after a second administration (if given), as well as to assess for adverse events. If the subject continues to meet criteria for severe or severe-complicated disease within the prior 24 hours at 3 days after the initial administration and then 3 days after the second administration (if given), the subject will be eligible for a repeat dose of PMT (same formulation as per initial randomization). If PMT administration is unable to be performed at 3 or 6 days following the first administration, then administration within 1 calendar day before or after those days will be permitted. Assessment for eligibility for an additional dose will be performed on the day of repeat administration. For subjects in the non-PMT arm, monitoring will be performed daily for three days after enrollment for adverse event assessment.

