**Figure 1: Allocation to Interventional Group Flow Diagram**

### 3.2. Study Endpoints

#### 3.2.1. Primary Study Endpoints

The primary outcome is resolution of symptoms associated with S/SC/F-CDI, listed below. The primary outcome will be satisfied when the subject is discharged from the hospital (not to hospice or palliative care) or, while the subject remains hospitalized, when the following criteria are met for 72 hours:

- If radiology study or studies performed, ileus/dilation/megacolon either not noted or noted as resolved (electronic medical record search words: “ileus”, “dilated”, “dilation”, or “megacolon”)
- Ileus/megacolon either noted as resolved by any provider documentation or not noted (electronic medical record search words: “ileus”, “megacolon”)
- WBC < 15,000 cells/uL
- Serum creatinine decreased, unchanged, or increased by  $\leq 0.2$  mg/dL over 72 hours (if not receiving continuous renal replacement therapy (CRRT) or hemodialysis (HD))
- Lactate  $\leq 2.2$  mmol/L (if measured by clinical care team)
- No vasopressors used (including epinephrine, norepinephrine, phenylephrine, or vasopressin)
- Temperature  $< 38.5$  °C and  $\geq 35.6$  °C
- < 8 bowel movements per day and < 600 mL unformed stool (if volume recorded)
- Meeting fewer than 3 systemic inflammatory response syndrome (SIRS) criteria (i.e., no more than two of the following: heart rate > 90 beats per minute; respiratory rate > 20 breaths per minute or PaCO2 < 32 mmHg; temperature > 38°C or < 36°C; WBC > 12,000 cells/uL, < 4,000 cells/uL, or > 10% immature (band) forms)

Discharge to hospice, need for bowel surgery (colectomy, diverting ileostomy), and death will count as failures. Subjects who undergo bowel surgery after initial PMT administration will not be eligible for additional administrations.

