### 5.2. Intervention Regimen

This study is a randomized, controlled, open label trial. Subjects will be screened to evaluate if they meet inclusion criteria for severe or severe complicated/fulminant CDI. If eligible, subjects will participate in the informed consent process. Following informed consent, subjects will be randomized to one of three arms: (1) standard of care antibiotics (no intervention), (2) PMT-upper GI administration plus standard of care antibiotics, or (3) PMT-lower GI administration plus standard of care antibiotics. In the intervention arms, subjects will then be eligible to receive up to two additional administrations of PMT (upper or lower GI) at 3-day intervals if they do not meet pre-defined criteria for clinical improvement for 24 hours (see [Section 2.1](#)). If PMT administration is unable to be performed on the scheduled days (3-day intervals), administration within 1 calendar day before or after those days will be permitted. Subjects will be assessed for eligibility for an additional dose on the day of repeat administration. Subjects will be followed until 180 days after their last PMT dose.

During the intervention period, following informed consent and randomization ([Section 3.1.2](#)), subjects in either intervention arm (not the standard of care control arm) will receive single-dose PMT administration, with PMT formulation determined per randomization. Administration of the product is described in [Section 5.7](#) below. Subjects will be eligible to receive up to two additional administrations of PMT (per same randomization) at 3 days and 6 days (+/-1 day) after the initial dose if they fail to meet criteria for clinical improvement ([Section 3.2.1](#)) and as long as they do not have bowel surgery. Antibiotics prescribed as part of routine clinical care for CDI will not be altered by the intervention.

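### Bowel surgery is the only subject-level safety criterion in the repeat-dose rule; the perforation and ANC < 1000 exclusions are not re-applied before PMT doses 2 and 3

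*Combined protocol and SAP*

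**What the plan says.** Section 6.2.4 sets two conditions for a further dose. The subject must still meet severe or severe-complicated criteria in the prior 24 hours, and there must have been no bowel surgery: "if the subject has not undergone bowel surgery, the subject will be eligible for an additional dose of PMT". It adds: "Subjects will be assessed for eligibility for an additional dose on the day of repeat administration". Section 5.2 allows doses 2 and 3 "as long as they do not have bowel surgery", and 3.2.1 says: "Subjects who undergo bowel surgery after initial PMT administration will not be eligible for additional administrations".

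The other repeat-dose passages turn on lack of improvement. Section 1.3 allows repeat dosing "if subjects fail to meet pre-established criteria for clinical improvement". Section 3.1.4 says that, with persisting disease, "the subject will be eligible for a repeat dose of PMT". Section 6.2.2 is similar. Sections 3.1 and 3.1.2 also turn on lack of improvement, but refer to 3.2.1, where the surgery bar stands.

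Section 4.2 excludes subjects with evidence of perforation at screening (exclusion 1) and subjects with ANC below 1000 cells/uL (exclusion 3). Table 3 marks the inclusion/exclusion review under Screening & Enrollment only, although it has a column that includes the retreatment days.

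**The concern.** Repeat doses of a live microbial product go to the subjects who are not improving. Two conditions that bar a first dose are not stated bars to a second or third, although 12.1 cites both exclusions as ways of limiting product risk.

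Perforation is the main worry. Ileus, dilation or megacolon is one of the findings that keeps a subject eligible (Table 2). Subjects with ileus are sent to the enema (3.1.6), and 12.1 lists perforation among the most severe possible risks of lower administration.

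New neutropenia matters mainly for subjects who stay eligible on a criterion other than WBC ≥ 15,000. For them the rule can work the wrong way. A WBC below 4,000 is itself a SIRS item, and three SIRS items qualify as severe-complicated, so new leukopenia can help a subject qualify for another dose.

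**Working it through.** **1. Which passages state a safety bar.** Eight sections say who may have a repeat dose.

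| Section | Surgery bar | Perforation or ANC bar |
|---|---|---|
| 3.2.1, 5.2, 6.2.4 | stated | none |
| 3.1, 3.1.2 | by reference to 3.2.1 | none |
| 1.3, 3.1.4, 6.2.2 | none | none |

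So 3 + 2 = 5 of 8 sections reach the surgery bar, and 0 of 8 name perforation or ANC.

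**2. Whether the entry exclusions carry forward.** Exclusion 1 is limited by its wording to screening. Exclusion 3 has no such limit, but the only scheduled review of exclusions is on Day 1. The pregnancy exclusion is timed to consent and the first administration, which also suggests that 4.2 governs entry and the first dose. The same-day assessment in 6.2.4 is of eligibility for an additional dose and does not cite 4.2.

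**3. Time from the Day 1 check to doses 2 and 3.** Inputs are Table 3 and its footnote: first dose on Day 1 or Day 2; retreatment on Days 4 and 7, or Days 5 and 8, each ± 1 day.

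- First dose Day 1: dose 2 on Days 3–5 (2–4 days elapsed); dose 3 on Days 6–8 (5–7 days).
- First dose Day 2: dose 2 on Days 4–6 (3–5 days); dose 3 on Days 7–9 (6–8 days).
- Combined: dose 2 at 2–5 days and dose 3 at 5–8 days, so 2 to 8 days overall.
- Section 6.2.4 can also be read as timing dose 3 from the actual second dose (3 ± 1 days later). Dose 3 then falls between Day 3 + 2 = Day 5 and Day 6 + 4 = Day 10, and the overall range becomes 2 to 9 days.

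**4. Exposure.** Section 4.5 plans 30 subjects per arm. Two PMT arms × 30 = 60 subjects, and 60 × 2 = 120 possible repeat doses. This bounds all repeat dosing, on the assumption that every PMT subject fails to improve twice. It does not estimate how many subjects would have a new perforation or neutropenia. The documents give no rate of repeat dosing or of either event.

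**5. What else could stop a dose.**

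- Section 9.4 halts administration for an event that is serious, unexpected and related, and separately for any suspected or proven infection judged product-related. A perforation judged unrelated does not trigger it. Nor does a low ANC that fails any of the three tests, unless there is also a product-related infection.
- Section 6.6 lets the subject withdraw, and lets the investigator or sponsor discontinue a subject for adverse events or safety. This is discretionary.
- The safety endpoints listed for the three days after dosing (3.2.3.2) include neither perforation nor neutropenia, though general adverse event recording applies (9.2). Section 7.4 adds no study laboratory tests, so no ANC is mandated before a repeat dose.

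**The case against.** The strongest reply is that several layers already protect these subjects. They are inpatients, monitored daily, assessed on the day of each repeat dose and dosed by licensed professionals. Section 9.1.3 makes bowel injury an event of special interest during the 60-minute bedside observation. Section 9.2 sets relatedness at a reasonable possibility, and perforation is not among the expected events in 9.1.4, so a perforation soon after an enema would probably trigger the 9.4 halt. The infection halt requires neither seriousness nor unexpectedness. Section 3.1.2 asks for a clinically appropriate route, which an enema into a perforated colon would hardly satisfy. A separate Drug Safety Monitoring Plan and a DSMB Charter are cited and may contain a dose-day check; neither can be seen.

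Most of this stands, and it narrows the gap. It does not close it. The route phrase mainly concerns the choice of product, and daily monitoring detects events without stating that a given finding bars a dose.

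A reader might infer that surgery is the only provision in the protocol that can stop a repeat dose. The documents do not support that, because 9.4 and 6.6 can both do so. A reader might also infer that the protocol directs a dose despite perforation. It does not: the rule permits a repeat dose and does not require one, and a clinician who knew of a perforation would probably withhold it.

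**Conclusion.** The point holds as a gap in the repeat-dose rule. Bowel surgery is the only subject-level safety criterion in that rule, and nothing re-applies the perforation or ANC exclusion in the 2 to 8 days (or 9) between the Day 1 check and doses 2 and 3. What remains is a perforation judged unrelated and managed without surgery, or a new ANC below 1000 that is not a serious, unexpected and related event. For these, protection is discretion alone.

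The textual finding is firm. The clinical consequence cannot be sized, and 120 repeat doses is a ceiling on all retreatment. The conclusion assumes that the unseen monitoring documents contain no dose-day check. New comfort-directed care and new symptomatic COVID-19 are likewise not stated bars but matter less; withdrawal and ongoing consent (12.4) largely cover the former. The change should be made because it is cheap and concerns subject safety.

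**What to change.** In 6.2.4, extend the existing day-of-dose assessment. A repeat dose is given only if chart review shows:

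- no evidence of bowel perforation;
- no ANC below 1000 cells/uL on the latest available clinical value;
- no change to comfort-directed care;
- no new symptomatic COVID-19.

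Cross-refer to 6.2.4 from the other seven repeat-dose sections (1.3, 3.1, 3.1.2, 3.1.4, 3.2.1, 5.2, 6.2.2). Add a Table 3 footnote for this check on each retreatment day: Days 4 and 7, or Days 5 and 8 if the first dose is on Day 2, ± 1 day. Leave exclusion 1 as it is. It is an entry criterion, and a perforation after randomisation should not make a subject appear ineligible at enrolment.

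The cost is wording only. The assessment is already required, and 7.4 already takes laboratory values from the clinical record, so no test is added. A few repeat doses may be withheld. The ANC check adds nothing when the care team has obtained no new value since screening.
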